### Partner support & Financial Control

16. Chal mar ayaki mar jaherani?
  - m. En kod kute mag ayaki
  - n. Oonge kod kute mag ayaki
  - o. Ok ong'ere
  - p. Aonge ng'ato sani
17. Jaherani ne otimre nade kane owinjo ni iyach?
  - a. Ne Omor
  - b. Ne entie kanyo
  - c. Ne ok omor
  - d. Ok ang'eyo
  - e. Aonge jaherana sani
18. En ng'a ma chiwo yore kaka onego uti kod pesa e odu?
  - g. Jaherana, seche duto
  - h. Jaherana ngenyne ma oloya
  - i. Jaherana kod an maromre
  - j. An ngenyne moloyo jaherana
  - k. An, Seche duto.
  - l. Aonge jaherana sani
19. Yuto maru e juma
  - f. Tin ne mia 500
  - g. Kind mia 500-750
  - h. Kind mia 750-1,000
  - i. Kind 1,000-2,500
  - j. Oingo 2,500
20. Chunya chandre nikech aonge pesa moromo ma anyalo chopo godo hospital kata ma nyathina nyalo yudo godo thieth?
  - a. Ayiego Ahinya
  - b. Ayiego
  - c. Adagi
  - d. Adagi Ahinya

### Partner Support

21. Be ineno ka en gima ber mondo jaherani omiyi sir e yore gi, kaka ?

|  | Ok
ochuno
ahinya |  | Ok
ochuno | Ochuno
matin | Ochuno
ahinya | Aonge kod jaherana |
|--|------------------------|--|--------------|-----------------|------------------|--------------------|
| 21a Dhi kodi kanyakla achiel e thieth mar PMTCT?               |                        |  |              |                 |                  |                    |
| 21b. Miya pesa mar dhi godo hospital?                          |                        |  |              |                 |                  |                    |
| 21c. Miya paro kaka inyalo bedo gi ngima maber ndalo ma iyach? |                        |  |              |                 |                  |                    |
| 21d. Konyi kod tije mag ot mondo iywe?                         |                        |  |              |                 |                  |                    |
| 21e. Konyi kod tije mag ot mondo idhi e thieth mar PMTCT?      |                        |  |              |                 |                  |                    |
| 21f. Paroni mondo imwony yath?                                 |                        |  |              |                 |                  |                    |
| 21g. Paroni mondo iluw thieth kaka daktari ne owacho?          |                        |  |              |                 |                  |                    |
| 21h. Miya pesa mar nyiew yath kata vitamins?                   |                        |  |              |                 |                  |                    |
| 21i. Dhi nywol?  |                        |  |              |                 |                  |                    |
| 21j. Miya mijing'o   |                        |  |              |                 |                  |                    |

22. Gin yore mage madiher mondo jaherani osiri godo ndalo ma iyach?

|  | Ne
onge
geno | Ok
ongere | Ne an
kod
geno | Aonge
kod
jaherana |
|--|--------------------|--------------|----------------------|--------------------------|
|  |                    |              |                      |                          |

|  |  |  |  |  |
|--|--|--|--|--|
| 22a Dhi kodi kanyakla achiel e thieth mar PMTCT?               |  |  |  |  |
| 22b Miya pesa mar dhi godo hospital?                           |  |  |  |  |
| 22c. Miya paro kaka inyalo bedo gi ngima maber ndalo ma iyach? |  |  |  |  |
| 22d. Konyi kod tije mag ot mondo iywe?                         |  |  |  |  |
| 22e. Konyi kod tije mag ot mondo idhi e thieth mar PMTCT?      |  |  |  |  |
| 22f. Paroni mondo imwony yath?                                 |  |  |  |  |
| 22g. Paroni mondo iluw thieth kaka daktari ne owacho?          |  |  |  |  |
| 22h. Miya pesa mar nyiew yath kata vitamins?                   |  |  |  |  |
| 22i Dhi nywol?   |  |  |  |  |
| 22j. Miya mijing'o   |  |  |  |  |

### Depression

Kiyie to yier dwoko machiegni gi kaka ne iwinjo kuom ndalo 7 mosekalo,ok kawuono kende.

23. Ase ngiyo mbele kod mor mar gik mangeny
  - e. Kaka asebedo ga katimo
  - f. Matin kaka asebedo katimo
  - g. Matin ahinya molooyo kaka asebedo
  - h. Ak asebedo
24. Weche ka odhi marach to asebedo ka ajilaumu
  - e. Eeh, Ngenyne
  - f. Eeh , seche moko
  - g. Ok seche te
  - h. Ooyo, podi
25. Asebedo ka awinjo ka aluor ma onge gima omiyo
  - e. Eeh,seche mangeny
  - f. Eeh, seche moko
  - g. Ooyo, ok ahinya
  - h. Ooyo,podi
26. Asebedo ma ok amor, ma asebedo ka aywak
  - e. Eeh, seche mangeny
  - f. Eeh, seche moko
  - g. Mana seche moko
  - h. Ooyo,podi
27. Paro mar hinyruok an awuon ase bedogodo
  - i. Eeh, Ngenyne
  - j. Seche moko
  - k. Mana seche moko
  - l. Podi

### Risk of Violence

Kuom weche gi chakre (27-30), yier duoko manyiso kaka gik moko osetimre kuom dweche 12 mosekalo

|  | Podi | Ok ahinya | Seche moko | Ngenyne |
|--|------|-----------|------------|---------|
| 28. Kuom dweche 12 mosekalo, be jaherani ose yanyi kata miyi mondo iwinj marach ne in iwuon? |      |           |            |         |
| 29. Kuom dweche 12 mosekalo , be jaherani ose goyi, gweyi,ywayi piny kata rodhi?             |      |           |            |         |
| 30. Kuom dweche 12 mosekalo , be jaherani ose goyo, gweyo,ywayo piny kata rodho nyathini?    |      |           |            |         |
| 31. Kuom dweche 12 mosekalo, be jaherani osechuni mondo uriwru kode to ne ok idwa?           |      |           |            |         |

### PMTCT Knowledge

Kiyie to yier duoko maberni

32. Ndalo ma a yach, onego ayud pim mar viral load

- g. Adagi, pim mar viral load itimo mana bang nywol
  - h. Kind achiel kod nyadiriyo
  - i. Nyadidek.
  - j. Ok angeyo
33. Ndalo ma l yach, dwarre ni mon man kod kute mag ayaki omwony yath mar ART seche ma ok giwinj maber.....Adier / miriambo
34. Dwarore ni mondo adhi clinic mar ANC nyadidi?
- e. 2
  - f. 3
  - g. 4
  - h. 5

#### PMTCT Motivation and self-efficacy

Kiyie to nysis kaka iyie kata idagi kod weche gi

|   | Adagi Ahinya | Adagi | Man e diere | Ayie | Ayie Ahinya |
|---|--------------|-------|-------------|------|-------------|
| 35. Angeyo ni anyalo luwora kod thieth kaka dwarore ndalo duto ma ayach, kata ka ji nitire machiegni.   |              |       |             |      |             |
| 36. En gima ber mondo adhi anywol e od thieth molooyo nywol dala.                                       |              |       |             |      |             |
| 37. Chunya chandore ni ok abiyudo gima biro ting'a ka tera e od thieth ka saa mar nywol ochopo          |              |       |             |      |             |
| 38. Dich moko machalo kaka tich, tije ot, rito nyathi nyalo mona mondo adhi e thieth mar ANC kod PMTCT. |              |       |             |      |             |
| 39. Dhi e thieth mar ANC/PMTCT en gima ber ahinya kuomi   |              |       |             |      |             |

|  | Adagi ahinya | Adagi | Man e diere | Ayie | Ayie Ahinya |
|--|--------------|-------|-------------|------|-------------|
| 40. Ne adeko biro e od thieth mondo ayud ANC nikech weche Covid 19   |              |       |             |      |             |
| 41. Ne adeko biro yudo nikech ngato e oda, kata an ne ok awinj maber, bende ne ok adwar ni mondo amii ngato tuo.                         |              |       |             |      |             |
| 42. Ok adwar biro e od thieth sani ahinya mondo Ayud thieth mar ANC nikech aluor yudo tuo mar Covid-19                                   |              |       |             |      |             |
| 43. Chunya ne chandre ni kadipo ni anywol e od thieth to tuo mar covid -19 nyalo maka kata nyathina                                      |              |       |             |      |             |
| 44. Wuoth mar biro e od thieth osebedo matek( kalure kod pesa mar wuoth, kata yudo yor wuoth kaka gari kata apiko) nikech weche covid 19 |              |       |             |      |             |

Erokamono ahinya kuom miwa saa mari kod duoko penjo.

## Appendix IIB. Delivery survey (within 4 weeks, Intervention and Control Sites)

### For interviewer to fill out:

Study ID: \_\_\_\_\_

Date of interview \_\_\_\_\_

Interviewer initials \_\_\_\_\_

### Delivery

1. Nyathini ne inyuolo kanye?
  - a. Od thieth
    - i. Mane, kon mane \_\_\_\_\_
  - b. Nyamrerwa
    - i. Mane, kon mane \_\_\_\_\_
  - c. Dala
  - d. Mamoko
    - i. Kiyie to ler ane \_\_\_\_\_
2. Ne okawi seche adi mondo inywol?
  - a. Matin ne seche 2
  - b. Seche 2-5
  - c. Seche 6-12
  - d. Mohingo seche 12
3. Bende in kata nyathi ne oyudo chadruok moro amora?
  - a. Eeh
    - i. Kiyie to ler ane gimane otimore ne mama kod nyathi yore: \_\_\_\_\_
  - b. Ooyo \_\_\_\_\_

### Partner status & Disclosure

4. Chal mari mar kenya?
  - a. Pok adi katedo
  - b. Ose kenda
  - c. Pok okenda to an an kod osiepna
  - d. Wapogore kod jaherana
  - e. Wawere kod jaherana
  - f. Chi liel
  - g. Mamoko, ler ane \_\_\_\_\_
5. Dak mari chal nade?
  - a. Aonge jaherana sani
  - b. Adak mopogore kod jaherana
  - c. Adak kamoro achiel kod jaherana
6. Jaherani ma sani e wuon nyathi?.....Eeh / Ooyo
7. Chal mari mar ayaki isenyiso ng'a??
  - a. Onge ng'ato ma asenyiso
  - b. Jaoda/jaherana
  - c. Ng'ato achiel kase anyuola
  - d. Ng'ato achiel kase osiepni
  - e. Ng'ato achiel kose janyuolni
8. Chal mar ayaki mar jaherani?
  - a. En kod kute mag ayaki
  - b. Oonge kod kute mag ayaki
  - c. Ok ong'ere
  - d. Aonge ng'ato sani
9. En ng'a ma chiwo yore kaka onego uti kod pesa e odu?
  - m. Jaherana, seche duto

- n. Jaherana ngenyine ma oloya
  - o. Jaherana kod an maromre
  - p. An ngenyine molooyo jaherana
  - q. An, Seche duto.
  - r. Aonge jaherana sani
10. Yuto maru e juma
- k. Tin ne mia 500
  - l. Kind mia 500-750
  - m. Kind mia 750-1,000
  - n. Kind mia 1,000-2,500
  - o. Oingo 2,500
11. Chunya chandre nikech aonge pesa moromo ma anyalo chopo godo hospital kata ma nyathina nyalo yudo godo thieth?
- a. Ayiego Ahinya
  - b. Ayiego
  - c. Adagi
  - d. Adagi Ahinya

#### Partner Support

12. Ndalo mane iyach jaherani ma dichwo bende nekonyi e yore gi, kaka?:

|  | Podi | Ok ahinya | Seche moko | Ngenyine |
|--|------|-----------|------------|----------|
| 12b. Miya pesa ma iting'i godo ka idhi e od thieth?                                  |      |           |            |          |
| 12c. Miya paro kaka inyalo bedo gi ngima maber ndalo ma iyach?                       |      |           |            |          |
| 12d. Konyi kod tije mag ot mondo iywe?   |      |           |            |          |
| 12e. Konyi kod tije mag ot mondo idhi e thieth mar PMTCT?                            |      |           |            |          |
| 12f. Paroni mondo imwony yath.   |      |           |            |          |
| 12g. Paroni mondo iluw thieth kaka daktari ne owacho.                                |      |           |            |          |
| 12h. Miya pesa mar nyiew yath kata vitamins?   |      |           |            |          |
| 12i. Chuora ne omiya mijingo ndalo mane a yach                                       |      |           |            |          |
| 12j. An kod chuora ne walemo kanyakla mondo atiek ich maber kendo mondo anyuol maber |      |           |            |          |

13. Bende ne udhi kod jaherani e thieth mar PMTCT kamoro achiel?
- a. Ooyo, ne ok odhi kat achiel
  - b. Ne odhi dichiel
  - c. Ne odhi diriyo
  - d. Ne odhi molooyo adek.
  - e. Aonge jaherana.
14. Ka #13 en Ooyo, en ang'o momiyi ne ok odhi?
- a. Ne entie e tich seche mane adhi e PMTCT \_\_\_\_\_ Eeh / Ooyo
  - b. Odak kendo otiyo mabor \_\_\_\_\_ Eeh / Ooyo
  - c. Chunya ne ok orwako bedo e od thieth \_\_\_\_\_ Eeh / Ooyo
  - d. Ne ok adwar ni mondo odhi \_\_\_\_\_ Eeh / Ooyo
  - e. Ne ok odwar dhi \_\_\_\_\_ Eeh / Ooyo
  - f. Ne en kod tije mamoko \_\_\_\_\_ Eeh / Ooyo
  - g. Mamoko, ler ane \_\_\_\_\_
15. Be jaherani madichwo ne okonyi sama ne idhi nyuol? Kiyie to yier dwoko miyiego.
- g. Aonge kod jaherana madichwo
  - h. Ooyo, Jaherana ma dichwo ne ok ochiwo kony moro a mora seche mane adhi nyuol.
  - i. Jaherana ma dichwo ne okonya kod pesa mar chopo hospital, ento ne ok ochopo.
  - j. Jaherana ne okowa e hospital seche mane muoch kaya.
  - k. Jaherana ne obiro nena e hospital bang ka ose nyuol nyathi.
  - l. Jaherana ne okowa e hospital seche mane muoch kaya kendo ne obiro nena e hospital bang ka ose nyuol nyathi

#### Depression

Kiyie to yier dwoko machiegni gi kaka ne iwinjo kuom ndalo 7 mosekalo,ok kawuono kende.

16. Ase ngiyo mbele kod mor mar gik mangeny
  - i. Kaka asebedo ga katimo
  - j. Matin kaka asebedo katimo
  - k. Matin ahinya molooyo kaka asebedo
  - l. Ak asebedo
17. Weche ka odhi marach to asebedo ka ajilaumu
  - i. Eeh, Ngenyne
  - j. Eeh , seche moko
  - k. Ok seche te
  - l. Ooyo, podi
18. Asebedo ka awinjo ka aluor ma onge gima omiyo
  - i. Eeh,seche mangeny
  - j. Eeh, seche moko
  - k. Ooyo, ok ahinya
  - l. Ooyo,podi
19. Asebedo ma ok amor, ma asebedo ka aywak
  - m. Eeh, seche mangeny
  - n. Eeh, seche moko
  - o. Mana seche moko
  - p. Ooyo,podi
20. Paro mar hinyruok an awuon ase bedogodo
  - a. Eeh, Ngenyne
  - b. Seche moko
  - c. Mana seche moko
  - d. Podi

#### Risk of Violence

Kuom weche gi chakre (19-22), ), yier duoko manyiso kaka gik moko osetimre kuom dweche 12 mosekalo.

|  | Podi | Ok Ahinya | Seche Moko | Ngenyne |
|--|------|-----------|------------|---------|
| 21. Kuom dweche 12 mosekalo, be jaherani ose yanyi kata miyi mondo iwinj marach ne in iwuon? |      |           |            |         |
| 22. Kuom dweche 12 mosekalo , be jaherani ose goyi, gweyi,ywayi piny kata rodhi?             |      |           |            |         |
| 23. Kuom dweche 12 mosekalo , be jaherani ose goyo, gweyo,ywayo piny kata rodho nyathini?    |      |           |            |         |
| 24. Kuom dweche 12 mosekalo, be jaherani osechuni mondo uriwru kode to ne ok idwa.?          |      |           |            |         |

#### PMTCT Knowledge

25. Bende ng'a mamiyo nyalo gengo nyathine kuom yudo kute mag ayaki e yore gi?
  - a. Muonyo yedhe duto mag ART ndalo ma iyach kod ka l dhodho nyathi.....Yes / No / DK
  - bDhi nyuol e hospital maloyo nyuol dala.....Yes / No / DK
  - c. Tiyo kod infant formula seche madwarore kod dhodho nyathi .....Yes / No / DK
  - d. Miyo nyathi nevirapine.....Yes / No / DK
  - e. Miyo nyathi Cotrimoxazole.....Yes / No / DK
  - e. Miyo nyathi chak mar dhiang kod tong kapok ochopo dweche auchiel mondo omi nyathi odong kotegno...Yes / No / DK
26. Dwarore ni nyathi oyud pim makwongo mar ayaki kaen
  - k. Ei wige ariyo bang nyuol
  - l. Ka en wige auchiel
  - m. Ka en kod dweche auchiel
  - n. Ka en ja dweche apar kod ariyo
  - o. Ka oseweyo dhoth

p. Okya

27. Dwarore ni nyathi mondo opim kute mag ayaki seche madwarore nyaka ochop kara ang'o":

- a. Dweche auchiel
- b. Dweche apar kod ariyo
- c. Dweche apar kod aboro
- d. Higni ariyo
- e. Ka nyathi oweyo dhoth

#### PMTCT Motivation

For each of the following, indicate the extent to which you agree or disagree with the statement.

SD=strongly disagree, D=disagree, N=neither agree nor disagree, A= agree, SA = strongly agree.

|   | Adagi Ahinya | Agadi | Man e diere | Ayie | Ayie Ahinya |
|---|--------------|-------|-------------|------|-------------|
| 28. Angeyo ni anyalo luwora kod thieth kaka dwarore seche ma nyathina pod tin kendo dhoth         |              |       |             |      |             |
| 29. Miyo nyathi yathe en gima maber kuoma   |              |       |             |      |             |
| 30. Kata ka nyathi ok dwa yath, to angeyo ni abiro miye yath kaka dwarore                         |              |       |             |      |             |
| 31. Ber mondo nyatho oyud pim mar viral seche duto ndalo mapod odhoth.                            |              |       |             |      |             |
| 32. Dich moko machalo kaka tich, tije ot, rito nyathi nyalo mona mondo oyud pim mar wige auchiel. |              |       |             |      |             |
| 33. Tero nyathi e thieth seche madwarore en gima ger ahinya.                                      |              |       |             |      |             |

|  | Strongly Disagree | Disagree | Neutral | Agree | Strongly Agree |
|--|-------------------|----------|---------|-------|----------------|
| 34. Chunya ne chandre ni kadipo ni anywol e od thieth to tuo mar covid -19 nyalo maka kata nyathina  |                   |          |         |       |                |
| 35. Chunya chandre ni ka atero nyathina e pim e od thieth to wanyalo yudo tuo mar covid -19  |                   |          |         |       |                |
| 36. Ndalo mane ayach, weche mag wuoth mondo adhi ayud thieth mar ANC ne netek(weche pesa mar wuoth, kata yudo gari/apiko) nikech weche covid 19      |                   |          |         |       |                |
| 37. Ndalo mane ayach, ne adeko, kata ne ok adhi a thieth mar ANC, kata dok kaw yath nikech ne ok awinj maber, kendo ne ok adwar ni mondo ami ji tuo. |                   |          |         |       |                |

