### PMTCT Knowledge

Please choose the best answer:

32. During pregnancy, I should receive viral load testing:
- Never, viral load testing is only conducted after delivery
  - Between 1 and 2 times.
  - At least three times.
  - Don't know
33. During pregnancy, it is recommended that HIV+ women take ART medications only if they are feeling unwell.....True / False
34. It is recommended that I attend a minimum of how many ANC appointments?
- 2
  - 3
  - 4
  - 5

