#### PMTCT Motivation

For each of the following, indicate the extent to which you agree or disagree with the statement.

SD=strongly disagree, D=disagree, N=neither agree nor disagree, A= agree, SA = strongly agree.

|   | SD | D | N | A | SA |
|---|----|---|---|---|----|
| 28. I know I can maintain perfect adherence to my medication while my baby is very young and breastfeeding.                       |    |   |   |   |    |
| 29. Giving my baby his/her medication is extremely important to his health  |    |   |   |   |    |
| 30. Even if s/he does not want to take it, I know that I'll be able to give every dose of his/her medication                      |    |   |   |   |    |
| 31. It is extremely important to get routine viral load tests while my baby is still breastfeeding.                               |    |   |   |   |    |
| 32. Other commitments – such as work, household duties, childcare – may prevent me from getting my baby tested by 6 weeks of age. |    |   |   |   |    |
| 33. Attending all of my child's appointments is extremely important to me.  |    |   |   |   |    |

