#### PMTCT Motivation

For each of the following, indicate the extent to which you agree or disagree with the statement.

SD=strongly disagree, D=disagree, N=neither agree nor disagree, A= agree, SA = strongly agree.

|   | SD | D | N | A | SA |
|---|----|---|---|---|----|
| 22. I know I can maintain perfect adherence to my medication while my baby is very young and breastfeeding.                       |    |   |   |   |    |
| 23. Giving my baby his/her medication is extremely important to his health  |    |   |   |   |    |
| 24. Even if s/he does not want to take it, I know that I'll be able to give every dose of his/her medication                      |    |   |   |   |    |
| 25. It is extremely important to get routine viral load tests while my baby is still breastfeeding.                               |    |   |   |   |    |
| 26. Other commitments – such as work, household duties, childcare – may prevent me from getting my baby tested by 6 weeks of age. |    |   |   |   |    |
| 27. Attending all of my child's appointments is extremely important to me.  |    |   |   |   |    |

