#### PMTCT Motivation

Kuom weche gi, ere ma iyiego kata idagi.

SD=strongly disagree, D=disagree, N=neither agree nor disagree, A= agree, SA = strongly agree.

|   | Adagi Ahinya | Adagi | Man e diere | Ayie | Ayie Ahinya |
|---|--------------|-------|-------------|------|-------------|
| 22. Angeyo ni anyalo luwora kod thieth kaka dwarore seche ma nyathina pod tin kendo dhoth           |              |       |             |      |             |
| 23. Miyo nyathi yathe en gima maber kuoma   |              |       |             |      |             |
| 24. Kata ka nyathi ok dwa yath, to angeyo ni abiro miye yath kaka dwarore                           |              |       |             |      |             |
| 25. Ber mondo nyatho oyud pim mar viral seche duto ndalo mapod odhoth                               |              |       |             |      |             |
| 26. Dich moko machalo kaka tich, tije ot, rito nyathi nyalo mona mondo oyud pim mar dweche auchiel. |              |       |             |      |             |
| 27. Tero nyathi e thieth seche madwarore en gima ger ahinya   |              |       |             |      |             |

|  | Adagi ahinya | Adagi | Man e dierel | Ayie | Ayie Ahinya |
|--|--------------|-------|--------------|------|-------------|
| 28. Chunya chandre ni ka atero nyathina e pim e od thieth to wanyalo yudo tuo mar covid -19  |              |       |              |      |             |
| 29. Weche mag wuoth dhi kendo duogo ka aa e od thieth(weche pesa kata yudo gari/apiko) kalure kod tuo mar covid 19 ne omiyo adeko, kata koso yudo thieth |              |       |              |      |             |
| 30. Ne adeko yudo thieth kata dhi e od thieth mondo,nikech ne atuo kendo ne ok adwa ni mondo ami ji tuo  |              |       |              |      |             |

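### Luo versions of four patient survey items differ in meaning from the English, so knowledge and motivation measures combined across languages would mix different questions

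*Combined protocol and SAP*

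**What the plan says.** Appendix II provides the participant surveys in English, Swahili and Luo. Four items are at issue.

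- **Viral load motivation** (delivery item 31, 6-month item 25). English: "It is extremely important to get routine viral load tests while my baby is still breastfeeding". Luo, identical at both visits: "Ber mondo nyatho oyud pim mar viral seche duto ndalo mapod odhoth".
- **ART knowledge** (enrolment item 33, True/False). English asks whether it is recommended that HIV-positive women "take ART medications only if they are feeling unwell". The Luo item reads "omwony yath mar ART seche ma ok giwinj maber".
- **Infant testing motivation** (6-month item 26). English says other commitments "may prevent me from getting my baby tested by 6 weeks of age". The Luo item ends "mondo oyud pim mar dweche auchiel".

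Under Objective 1 specific methods, patient knowledge and motivation are named as potential mediators. They are to be compared before and after the intervention and between arms, and examined as predictors of PMTCT completion by logistic regression. Objective 2 reuses the same mediation methods. Neither section mentions survey language, stratification by language or a check that items are equivalent across languages.

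**The concern.** These measures are meant to show how HITSystem 2.1 works. Maternal viral load testing is one of its targeted outcomes, and items 31 and 25 are the only motivation items about it at delivery and 6 months. If a Luo respondent is asked about testing her child instead, her answer does not measure that construct. A knowledge item without its restricting word no longer cleanly separates women who know ART is continuous from those who do not. If answers are combined over languages, part of any difference in knowledge or motivation between women, sites or regions may come from the form. A pre-post change can also be distorted where the Luo wording itself changes between visits, as it does for infant testing (delivery item 32 against 6-month item 26).

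**Working it through.** The plan gives no figure to reproduce, so the check is a comparison of wordings. The Luo forms can largely be read from within the document, because other Luo phrases have printed English counterparts.

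1. **Who is tested in items 31 and 25.**
   - Luo delivery knowledge item 26, "Dwarore ni nyathi oyud pim makwongo mar ayaki kaen", is the counterpart of the English question on when the respondent's infant should have a first HIV test. There, *nyathi oyud pim* means the infant gets a test.
   - Luo enrolment item 32 has "onego ayud pim mar viral load", the counterpart of the English question on the woman's own viral load testing. There the verb is *ayud*, I receive.
   - Items 31 and 25 use *nyatho oyud*. Taking *nyatho* as a misprint of *nyathi*, the subject is the child. In the Swahili items the child appears only as the one still breastfeeding, as in English.

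2. **The missing *only* in item 33.**
   - English has the word, and Swahili has *pekee*.
   - The Luo forms write *mana* where English has *only*: in enrolment item 32, directly above, and in 6-month item 19.
   - Luo item 33 has no *mana*. Read literally, it says women should take ART at times when they do not feel well. A woman who knows ART is taken at all times could answer True without being mistaken.

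3. **Weeks or months in item 26.**
   - In the answer options of Luo delivery knowledge item 26, *wige auchiel* is the 6-week option and *dweche auchiel* the 6-month option.
   - The Luo 6-month motivation item has *dweche auchiel*. English and Swahili say six weeks there, and the Luo delivery version of the item (32) has *wige auchiel*.

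4. **Count of affected items by section.**
   - Enrolment knowledge, items 32–34: item 33, so 1 of 3.
   - Delivery motivation, items 28–33: item 31, so 1 of 6.
   - 6-month motivation, items 22–27: items 25 and 26, so 2 of 6.
   - All patient knowledge and motivation items: knowledge 3 + 8 + 3 = 14 (counting delivery item 25a–f as six) and motivation 5 + 6 + 6 = 17, total 31. Four of 31 is about 13%.

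5. **How many women could be involved.** The documents do not say which language is used where. Table 2 has 4 Siaya pairs, so 8 of 12 sites. Assume, for illustration, that every woman at those sites and no one else used the Luo form. The revised sample in the Objective 2 sample size section is 2 × 96 + 10 × 126 = 1,452.
   - If both sites that have stopped enrolling are in Siaya: 2 × 96 + 6 × 126 = 948, or 65%.
   - If neither is: 8 × 126 = 1,008, or 69%.
   - If only some Siaya women used Luo, the share falls in proportion.

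The same comparison shows one mismatch outside these scales. Luo 6-month SMS item 35 asks about the time since starting ANC, where English asks about the time since the birth.

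**The case against.** The strongest reply is that the documents do not show the harm.

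- **No answer key, sum score or scale definition is printed for patient items.** Site averages are specified only for providers. A reader might infer that Luo women who answer True to item 33 are scored wrong, or that pooled scores are already planned. Neither is stated. Combining across languages is an inference from the absence of any language split. This stands.
- **Item 26 may not be a Luo error.** A reader might take English as the standard. But the English item asks a woman at 6 months postpartum whether commitments may prevent a test by 6 weeks, which has already passed. Its wording matches delivery item 32 and looks carried over. The study also offers an infant PCR at the 6-month visit, so the Luo wording may fit that visit better. The documents show only that the versions disagree. This stands.
- **Item 33 turns on a fine reading.** Some Luo speakers may hear the restriction without *mana*. The page cannot settle this, so a Luo speaker should confirm it.
- **Administration may soften the problem.** Mentor mothers conduct the surveys, and staff are trained in standardized collection. They may clarify orally, but no such procedure for these items is described, and the printed wording remains. Translation certificates are listed as Appendix III and cannot be assessed here; a certificate would not change the printed items.
- **Most items are not challenged.** Four of 31 are affected. This is fair overall, but the share is larger in the short sections where they fall.

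None of this answers the difference in items 31 and 25, which the forms' own usage supports.

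**Conclusion.** The point holds as a discrepancy between printed forms that bears on secondary work. Items 31 and 25 ask Luo respondents about a different person's test. Item 33 lacks its restricting word, subject to confirmation by a Luo speaker. Item 26 is unreconciled between languages. Combining these items over languages would mix different questions.

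A reader might go further and conclude that the mediator and predictor analyses are biased. The documents do not support that: the scoring and the language used by each woman are not given, so neither the size nor the direction of any effect can be derived. Nor are the primary outcomes touched, since complete PMTCT comes from service records and detectable viral load from laboratory results. If Luo is used mainly in Siaya, the within-region pairing in Table 2 would leave language roughly balanced between arms. The likelier consequences would then be measurement error and scores confounded with region. The importance is low, but the correction is cheap and was still useful when the amended sample size text was written, with ten sites enrolling.

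**What to change.** Before further use, have a Luo speaker confirm and correct items 31/25 and 33. Decide which infant test 6-month item 26 is meant to ask about, and make all three languages agree. The 6-month SMS item 35 can be checked at the same time.

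Record form language and version for every survey. The survey headers carry only study ID, date and interviewer initials, so for past surveys these would have to be recovered from the paper forms.

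State in the analysis plan how patient knowledge and motivation are scored. For data already collected, leave enrolment item 33, delivery item 31 and 6-month items 25 and 26 out of any score combined across languages, or analyse them within language. A language covariate alone is not enough: language is probably confounded with region, so the term would absorb regional differences along with translation differences.

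The cost is a form correction, one extra recorded field and slightly shorter scales: 2 of 3 enrolment knowledge items, 5 of 6 delivery motivation items and 4 of 6 six-month motivation items would remain in the combined scores.
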